RLIC and Sham Conditioning	Remote limb ischemic conditioning will be achieved via blood pressure cuff inflation to 20 mmHg above resting systolic blood pressure up to 200 mmHg.  Sham conditioning will be achieved via blood pressure cuff inflation to 25 mmHg on the more involved thigh. Conditioning will involve 5 cycles of 5 minutes blood pressure cuff inflation followed by alternating 5 minutes of cuff deflation. Subjects will be blinded to their group assignment (RLIC or sham conditioning). Conditioning requires 45 minutes. RLIC or sham conditioning will be performed on visits 1-14.

Behavioral Training	
Three tasks will be used for behavioral training on visits 3-14.
 
 
1) Power training task (20-30 minutes)
 
2) Balance training task (15 minutes; rest breaks as needed)
 
3) Treadmill training (15 minutes)
 
 
Power Training: Prior to training and at the beginning of each training week, we will obtain 1 repetition maximum (1 RM) on each leg. 60-80% of the 1 RM will be used as training intensity with progression toward 80% based on that week's 1 RM. Training will involve unilateral and bilateral leg presses (Total Gym GTS, San Diego, CA), 3 times/week for 4 consecutive weeks (12 sessions). Each session will begin with 5 minutes of warm-up exercises. Each participant will perform 6 sets of 5-7 concentric extension contractions with maximum efforts, and with one-three minutes rest after each set.
 
Balance Task: The balance task requires subjects to stand on a movable platform (Stability Platform, model 16030L, Lafayette Instrument) and to keep the platform in a balanced, horizontal position. This task was selected because it can be easily modified to the appropriate level of difficulty in accordance with each subject's motor abilities.
 
Treadmill Training: We will use short burst interval treadmill training. We will use the self-selected and fast walking speeds determined by the 10-meter walk test as the training intensity for the child for each session. Short burst interval training will consist of 30 seconds fast followed by 30 seconds of slow walking. We chose this type of training since it closely resembles the walking performance of a child in the community.

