--	---

Order of Experiment/Study Visits	
This study involves 16 total visits. Participants will be in the study for up to 8 weeks. Please refer to Table 1 for a timeline of study visits.
 
Visit 1: We will provide informed consent and assent and gather demographic data. Next we will perform baseline assessments for the performance on the quadriceps power, EMG, balance, and walking.
 
Then, we will quantify power of bilateral knee extensor by recording peak knee extensors torque and electromyography of bilateral rectus femoris, vastus lateralis, and vastus medialis.
 
Next, we will gather measurements on balance task.
 
Next, we will assess walking performance using 10-meter walk test, 3-D gait analysis, and accelerometry.
 
Subjects will then be randomized to their treatment group. After randomization, subjects will undergo RLIC or sham conditioning (see RLIC and Sham Conditioning for the details). This visit will take approximately: 3 hours.
 
Visit 2: Subjects will undergo RLIC or sham conditioning This visit will take approximately: 1 hour.
 
Visit 3-14: Subjects will undergo RLIC or sham conditioning. Next, behavioral training will commence (power training task and balance training). The order of behavioral training task practice will be randomized. Visits 3-14 will occur every alternate business day. These visits will take approximately: 2-2.5 hours.
 
Visit 15: Subjects will complete post-testing which will include a) quadriceps power; b) EMG; c) balance task, and d) walking performance. Visit 15 will be on the next business day after visit 14. During this visit, participants will not receive RLIC or sham conditioning. This visit will take approximately: 2 hours.
 
Visit 16: Post-test performance assessment on power, EMG, balance, and walking will be performed after 4-weeks from the visit 15. Participants will not receive RLIC or sham conditioning during the follow-up visits. Participants will fill out a survey on the follow-up visit indicating whether they think that they received RLIC or sham treatment. This visit will take approximately: 2 hour.

Data Analysis	
Data will be analyzed using a mixed model ANOVA with time (pretest, posttest, and follow-up) as within subject factor and group (RLIC vs. sham treatment) as between subject factor.

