Safety Considerations & Monitoring	
The risks of participating in the rehabilitation intervention are minimal and are similar to the risks encountered during routine physical and occupational therapy services.
 
Conditioning:

	
The likely risks are:
 
 
1. Bruising on the conditioning thigh: To avoid bruising from the pressure cuff, participant's arm will be covered with a folded cotton pillowcase.
 
2. Discomfort: To avoid discomfort in the conditioning thigh during each conditioning cycle, we will ask the participant about discomfort. If the participant reports discomfort, we will reposition the pressure cuff on the thigh and allow the participant to move the thigh during 5-minutes of deflation cycle.
 
3. Pain or tingling on the conditioning arm: To avoid pain or tingling in the conditioning thigh during the conditioning cycle, we will ask the participant about pain and tingling. If the participant reports pain or tingling, we will reposition the pressure cuff on the thigh and allow the participant to move the thigh during 5-minutes of deflation cycle.
 
 
Power Training:
 
The likely risks are
 
 
1. Knee or thigh pain: To avoid the knee or thigh pain, participants will perform warm-up exercises for 5 minutes before starting the strengthening.
 
2. Muscle fatigue and delayed onset muscle soreness: Power training on every alternate day will allow sufficient time to recover from muscle fatigue and delayed onset muscle soreness.
 
 
Balance:
 
The less likely risks are
 
 
1. Falling from the balance board: To avoid falling from the balance board, participants will be permitted to use a handrail as needed for safety during balance task and up to two research team members will supervise the balance performance. Participants will also wear a gait belt for safety, which will help the research team member to catch the participant if they start to fall.
 
 
Treadmill:
 
The less likely risks are
 
 
1. Muscle fatigue and falling from the treadmill: To avoid falling from the treadmill, participants will be provided sufficient rest. Participants will also be allowed to use a handrail as needed and will also wear a gait belt for safety.
 
 
In order to monitor for further overall safety, we will continuously monitor lightheadedness, respiratory distress, cyanosis, and spasms. We will record and monitor heart rate, blood pressure, and oxygen saturation before, during, and after each session of RLIC. Sessions will be terminated if heart rate <60 bpm or >160 bpm, systolic BP <70 mmHg or >130mmHg, diastolic

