--	--

	BP <40 or >90 mmHg, O 2 saturation <90%, or if pain is >6 on 10-point Likert pain scale. Moreover, during the follow up session, all subjects will be asked questions about any adverse effects that resulted from participation in this study.
Investigators	PI: [name], PT
Number of Centers	1 center: East Carolina University
Key References	Please see the reference list.

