21. Hyngstrom, A. S., Murphy, S. A., Nguyen, J., Schmit, B. D., Negro, F., Guterman, D. D., & Durand, M. J. (2018). Ischemic conditioning increases strength and volitional activation of paretic muscle in chronic stroke: a pilot study. *Journal of Applied Physiology*, 124(5), 1140-1147.
22. Bird, S. P., Tarpenning, K. M., & Marino, F. E. (2005). Designing resistance training programmes to enhance muscular fitness. *Sports medicine*, 35(10), 841-851.
23. Cherry-Allen, K. M., Gidday, J. M., Lee, J. M., Hershey, T., & Lang, C. E. (2015). Remote limb ischemic conditioning enhances motor learning in healthy humans. *Journal of neurophysiology*, 113(10), 3708-3719.
24. Christie, A., & Kamen, G. (2010). Short-term training adaptations in maximal motor unit firing rates and afterhyperpolarization duration. *Muscle & Nerve: Official Journal of the American Association of Electrodiagnostic Medicine*, 41(5), 651-660.

25. Carroll, T. J., Selvanayagam, V. S., Riek, S., & Semmler, J. G. (2011). Neural adaptations to strength training: moving beyond transcranial magnetic stimulation and reflex studies. *Acta physiologica*, 202(2), 119-140.

Table 1: Order of the 16 study visits. Testing occurs on Study Visits 1, 15, and 16. Conditioning which involves 5 cycles of 5 minutes of lower extremity peripheral ischemia (or sham), alternating by 5 minutes of no ischemia, occurs on Study Visits 1-14. Training occurs on Study Visits 3-14 (Study Visits 4-14 occur every other business day, excluding weekends and holidays) and includes power, balance and treadmill training.

Assessment s	Visits															
	1 (D1)	2 (D2)	3 (D3 )	4 (D5 )	5 (D7 )	6 (D9)	7 (D11)	8 (D13)	9 (D15)	10 (D17)	11 (D19)	12 (D21)	13 (D23)	14 (D25)	15 (D26 )	16 (4 weeks from visit 15)
Consent/ Demographic details	✓															
Pre-testing	✓															
Conditioning (RLIC/ Sham)	✓	✓	✓	✓	✓	✓	✓							✓		
Training			✓	✓	✓	✓	✓							✓		
Post-testing														✓	✓	✓

\*D= business day

1. Pre-testing includes: Performance on the- 1) Power task, and 2) balance task, and 3) walking task.
2. Training includes: Training on the- 1) Bilateral Knee Extensor Strengthening, 2) Balancing task on the balance board, and 3) Short burst treadmill training.
3. Post-testing includes: Performance on the- 1) Power task, 2) balance task, and 3) walking task.

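### The only general adverse-effect question to all children comes at Visit 16, about 9 weeks after first conditioning, so between-session harms and those of early leavers can go unrecorded

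*Combined protocol and SAP*

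**What the plan says.** Safety Considerations & Monitoring ends with the one general enquiry about harm: "during the follow up session, all subjects will be asked questions about any adverse effects that resulted from participation in this study". Order of Experiment/Study Visits uses follow-up for Visit 16, whose assessments "will be performed after 4-weeks from the visit 15".

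Exposure starts much earlier. At Visit 1, "After randomization, subjects will undergo RLIC or sham conditioning", and the conditioning section adds that "RLIC or sham conditioning will be performed on visits 1-14". Training runs over Visits 3 to 14.

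The safety section also describes monitoring within sessions:

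- For the cuff, "during each conditioning cycle, we will ask the participant about discomfort", with a similar question on pain and tingling.
- Staff watch continuously for four acute signs: lightheadedness, respiratory distress, cyanosis and spasms.
- Heart rate, blood pressure and oxygen saturation are recorded around each RLIC session. Sham sessions are not mentioned in that sentence.
- Sessions end at stated vital-sign limits or at a pain score above 6.

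The risks the section lists as likely include bruising under the cuff, knee or thigh pain, and "Muscle fatigue and delayed onset muscle soreness". For these it gives preventive steps.

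The available text has no start-of-visit adverse-event question, no symptom log or grading, and no enquiry at withdrawal. Table 1 has no adverse-event row, and Data Analysis has no safety summary.

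**The concern.** In-session monitoring is aimed at what happens while the child is in the laboratory. Delayed soreness by its nature comes later, and bruising or knee pain may be noticed only at home. On the stated plan, the first time every child is asked about such things is Visit 16. By then a child aged 6 to 13 has to recall up to 14 conditioning and 12 training sessions.

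Two further gaps add to this. A child who stops before Visit 16, possibly because of a harm, never reaches the general question. A symptom reported during a cuff cycle leads to an adjustment of the cuff, but the text does not say that it is written down.

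What is at stake is the tolerability record of a new use of RLIC in children. The arms differ widely in cuff pressure (20 mmHg above resting systolic pressure, against 25 mmHg for sham), so readers will want to know how each was tolerated. A short list of harms could then reflect when the question was asked as much as what occurred.

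**Working it through.** **1. The plan's own figure.** Order of Experiment/Study Visits puts participation at up to 8 weeks, which is 56 days. The schedule should reproduce this.

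**2. Inputs from Table 1.** Visit 1 is D1, Visit 14 is D25, Visit 15 is D26 and Visit 16 is 4 weeks after Visit 15. The footnote says "D= business day", and the caption says that "Study Visits 4-14 occur every other business day, excluding weekends and holidays". Twelve training visits from D3 in steps of two end at 3 + 2 × 11 = D25, so the table agrees with itself.

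**3. First conditioning to the general question, Table 1.**

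- D1 to D26 is 26 − 1 = 25 business days. 25 / 5 = 5.0 weeks, or 35 calendar days, whatever the starting weekday.
- Adding 4 weeks: 35 + 28 = 63 days, and 63 / 7 = 9.0 weeks.
- One or two holidays (an assumption) lengthen this to 64 to 67 days, or 9.1 to 9.6 weeks.

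**4. The same interval on the other reading.** Behavioral Training describes three sessions a week for 4 consecutive weeks. Taking this as Monday, Wednesday and Friday (an assumption):

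- Visit 1 on a Monday: Visit 3 is that Wednesday, Visit 14 is day +28 and Visit 15 is day +29. Visit 16 is 29 + 28 = 57 days, or 8.1 weeks.
- Visit 1 on a Thursday: Visit 3 is the next Monday, Visit 14 is day +29 (a Friday) and Visit 15 is day +32. Visit 16 is 32 + 28 = 60 days, or 8.6 weeks.
- All five starting weekdays fall within 57 to 60 days.

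Neither reading gives the stated 8 weeks.

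**5. Last conditioning to the general question.** Visit 14 to Visit 15 is one business day, which is 1 day, or 3 across a weekend. Adding 28 gives 29 to 31 days.

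**6. What is asked or recorded, and when.**

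| Type of effect | In session | Before Visit 16, between sessions | If the child leaves early |
|---|---|---|---|
| Cuff discomfort, pain, tingling | Asked; recording not stated | No question stated | In-session questions only |
| Lightheadedness, respiratory distress, cyanosis, spasms | Observed; recording not stated | No question stated | In-session observation only |
| Vital signs | Recorded (RLIC named, sham not) | Not applicable | Recorded while attending |
| Bruising, knee or thigh pain, delayed soreness | Prevention steps; no specific question outside cuff use | No question stated | No question stated |

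**7. What asking at every visit would change.** On Table 1 without holidays, successive visits up to Visit 15 are one or two business days apart, which is 1 to 4 calendar days. The longest recall before Visit 15 would fall from about 9 weeks to 4 days. Only the 4 weeks between Visits 15 and 16 would remain long.

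**The case against.** The strongest reply is that the follow-up question is an addition to real in-session safeguards. Children are asked about cuff symptoms, watched throughout, measured, and protected by session limits. A child who later withdraws was still observed at every session attended. Staff see the child every second business day and handle the thigh where the cuff goes, so bruises may be seen and complaints heard. All of this stands. A reader might infer that short-lived harms are simply missed or that nobody asks before Visit 16, and the documents do not support that. What they lack is a general question before Visit 16 and a stated record of symptoms.

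A reader might also infer that early leavers bias a between-arm comparison of harms. No such comparison is planned: the listed outcomes are power, EMG, balance and walking. Nor would an upper confidence limit for zero reports among 12 children measure the problem. It depends only on the number asked, and would be the same if all 12 were asked at every visit and none reported anything.

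Two cautions concern wording. The follow-up sentence refers to effects that resulted from participation, but it summarises the questions and does not give them, so it does not prove that children must judge cause before answering. The vital-signs sentence may use RLIC as shorthand for both arms. Consent pages are not in the public text, so instructions to families about reporting problems may exist there.

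**Conclusion.** The point holds in a limited form. Acute effects during sessions are covered by questions, observation and limits, although only vital signs are said to be recorded and equal recording in the sham arm is not assured. Effects arising between sessions have no planned general question until about 9.0 weeks after first conditioning by Table 1 (8.1 to 8.6 weeks at three sessions a week) and 29 to 31 days after the last. Children who leave before Visit 16 have none. Such harms can therefore be missed or poorly recalled. The documents do not allow an estimate of how many.

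This assumes that the follow-up session means Visit 16. The Visit 16 paragraph uses the term in the singular and once in the plural, but Data Analysis separates posttest from follow-up, which supports that reading. If Visit 15 were meant, the interval from first conditioning would be 35 days and the gap for early leavers would remain.

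This is an inexpensive improvement to safety ascertainment. It does not affect the efficacy analysis.

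**What to change.** - At the start of each of Visits 2 to 16, ask one standard open question on whether anything has happened since the last visit, with the same wording in both arms. Ask it also at withdrawal.
- Log the answers, and any symptom raised or seen during a session, with onset, duration and severity, regardless of presumed cause.
- State that session monitoring is recorded for RLIC and sham alike.
- Report counts by arm descriptively.
- Name Visit 16 explicitly if that is the follow-up session meant, and reconcile the stated 8 weeks of participation with Table 1 and with the three-times-a-week wording.

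The cost is one log form and, assuming about a minute per question, 15 minutes per child over 15 existing visits. For 24 children that is 15 × 24 = 360 minutes, or 6 hours in all, plus a brief contact for each child who withdraws. No visit is added.

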21. Hyngstrom, A. S., Murphy, S. A., Nguyen, J., Schmit, B. D., Negro, F., Guterman, D. D., & Durand, M. J. (2018). Ischemic conditioning increases strength and volitional activation of paretic muscle in chronic stroke: a pilot study. *Journal of Applied Physiology*, 124(5), 1140-1147.
22. Bird, S. P., Tarpenning, K. M., & Marino, F. E. (2005). Designing resistance training programmes to enhance muscular fitness. *Sports medicine*, 35(10), 841-851.
23. Cherry-Allen, K. M., Gidday, J. M., Lee, J. M., Hershey, T., & Lang, C. E. (2015). Remote limb ischemic conditioning enhances motor learning in healthy humans. *Journal of neurophysiology*, 113(10), 3708-3719.
24. Christie, A., & Kamen, G. (2010). Short-term training adaptations in maximal motor unit firing rates and afterhyperpolarization duration. *Muscle & Nerve: Official Journal of the American Association of Electrodiagnostic Medicine*, 41(5), 651-660.

25. Carroll, T. J., Selvanayagam, V. S., Riek, S., & Semmler, J. G. (2011). Neural adaptations to strength training: moving beyond transcranial magnetic stimulation and reflex studies. *Acta physiologica*, 202(2), 119-140.

Table 1: Order of the 16 study visits. Testing occurs on Study Visits 1, 15, and 16. Conditioning which involves 5 cycles of 5 minutes of lower extremity peripheral ischemia (or sham), alternating by 5 minutes of no ischemia, occurs on Study Visits 1-14. Training occurs on Study Visits 3-14 (Study Visits 4-14 occur every other business day, excluding weekends and holidays) and includes power, balance and treadmill training.

Assessment s	Visits															
	1 (D1)	2 (D2)	3 (D3 )	4 (D5 )	5 (D7 )	6 (D9)	7 (D11)	8 (D13)	9 (D15)	10 (D17)	11 (D19)	12 (D21)	13 (D23)	14 (D25)	15 (D26 )	16 (4 weeks from visit 15)
Consent/ Demographic details	✓															
Pre-testing	✓															
Conditioning (RLIC/ Sham)	✓	✓	✓	✓	✓	✓	✓							✓		
Training			✓	✓	✓	✓	✓							✓		
Post-testing														✓	✓	✓

\*D= business day

1. Pre-testing includes: Performance on the- 1) Power task, and 2) balance task, and 3) walking task.
2. Training includes: Training on the- 1) Bilateral Knee Extensor Strengthening, 2) Balancing task on the balance board, and 3) Short burst treadmill training.
3. Post-testing includes: Performance on the- 1) Power task, 2) balance task, and 3) walking task.
